**8.1.1.4 Visit 4 (Week 48  $\pm$ 28 Days [End of Stage 1/Start of Stage 2])**

The subject will return to the site for visit 4. Visit 4 will proceed as follows:

- Record any adverse events occurring since last visit, and any that occur during this visit
- Record any changes in concomitant medications
- Physical examination
- Collect any unused study drug
- Study Drug Dosing Diary review and collection: The diary will be collected and reviewed
- Height and weight
- Vital signs (including systolic and diastolic blood pressure, radial pulse rate, and body temperature): performed after the subject has been in a sitting position for 3 - 5 minutes
- Complete the following ophthalmological assessments:
  - [REDACTED]
  - Ophthalmoscopy examination
  - BCVA and refraction
  - Slit-lamp examination - Slit-lamp examination should precede [REDACTED] measurement

- Slit-lamp photography. The Reading Center manual should be referenced for detailed instructions regarding macro photography
- OCT/Fundus photography - Anterior and posterior segment OCT and fundus photography will be performed. The Reading Center manual should be referenced for detailed instructions
- Humphrey visual fields
- [REDACTED]
- [REDACTED]
- MNREAD
- Blood draw for clinical laboratory evaluations
  - [REDACTED]
  - Serum  $\beta$ -HCG, as applicable (sample taken only for female subject of childbearing potential)
  - Hematology and biochemistry
- Urinalysis
  - [REDACTED]
  - [REDACTED]
- Dispense open-label ataluren and Study Drug Dosing Diary
  - TID dosing 10 mg/kg, 10 mg/kg, 20 mg/kg (morning, midday, evening)
- Schedule the Visit 5

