## 8.2 Visit 8 (Week 144±28 Days – End of Treatment/Start of Sub-study)

The subject will return to the site for Visit 8 (Week 144). Additionally, any subject who discontinues early from the parent study should complete the Visit 8 assessments and return in 4 weeks for follow-up assessments.

This visit will be considered the end of the parent study and the beginning of the sub-study. Subjects should have taken their final dose of study drug for the parent study the night before the clinic visit.

Visit 8 will proceed as follows:

- Record any adverse events occurring since last visit and any that occur during this visit
- Record any changes in concomitant medications
- Collect any unused study drug
- Study Drug Dosing Diary review and collection: The diary will be collected and reviewed
- Physical examination
- Height and weight
- Vital signs (including systolic and diastolic blood pressure, radial pulse rate, and body temperature): performed after the subject has been in a sitting position for 3 - 5 minutes
- Complete the following ophthalmological assessments:
  - [REDACTED]
  - Ophthalmoscopy examination
  - BCVA and refraction
  - Slit-lamp examination - Slit-lamp examination should precede [REDACTED] measurement.
  - Slit-lamp photography. The Reading Center manual should be referenced for detailed instructions regarding macro photography.
  - OCT/Fundus photography - Anterior and posterior segment OCT and fundus photography will be performed. The Reading Center manual should be referenced for detailed instructions.
  - Humphrey visual fields
  - [REDACTED]

- [REDACTED]
- MNREAD
- Blood draw for clinical laboratory evaluations:
  - Hematology and biochemistry
  - Serum  $\beta$ -HCG, as applicable (sample taken only for female subjects of childbearing potential)
  - [REDACTED]
- Urinalysis
- No study drug will be dispensed at this visit for subjects that do not consent to the sub-study. Subjects not continuing into the sub-study should return to the clinic in 4-weeks ( $\pm 7$  days) for their Follow-up visit.

For all subjects that choose to participate in the open-label sub-study, in addition to the Visit 8 assessments listed above, the following will need to be completed:

- Obtain written informed consent/assent
- Dispense open-label ataluren and Study Drug Dosing Diary, and review administration instructions
  - TID dosing 10 mg/kg, 10 mg/kg, 20 mg/kg (morning, midday, evening)
- Schedule Visit 9 in 24 weeks  $\pm 28$  days

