## 10 WITHDRAWAL OF SUBJECTS

All subjects who receive study drug should remain in the study whenever possible. However:

- The subject has the right to withdraw consent and discontinue study drug at any time.
- If the subject's condition substantially worsens after initiating study drug, the subject will be carefully evaluated by the investigator. The subject will be withdrawn from treatment if continuing would place them at risk.
- The investigator may withdraw the subject from study drug, if, in the investigator's clinical judgment, it is not in the subject's best interest to continue.
- If the subject becomes significantly noncompliant with study drug administration, study procedures, or study requirements. In this event, the subject should be withdrawn from study drug when the circumstances surrounding noncompliance increase risk to the subject or are anticipated to substantially compromise the interpretation of study results.
- The subject may be withdrawn from this study in circumstances where the masking is intentionally or accidentally broken.
- This study may be discontinued by the relevant regulatory authority, IRB/EC, and/or PTC Therapeutics at any time.

The date study drug is discontinued and the reason for discontinuation will be recorded in the source documents and in the eCRF. The PTC medical monitor (and designee) should be informed via e-mail of when a subject discontinues study drug.

When study drug is discontinued (regardless of the reason), the investigator is expected to capture all of the evaluations required at the EOS/ET Visit and any additional evaluations should be completed that may be necessary to ensure that the subject is free of untoward effects. The subject should be encouraged to seek appropriate follow-up for any continuing health problems.

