## 11.3 General Statistical Considerations

Two separate analyses will be conducted, one for the double-masked phase (Day 1 through Week 48), and the second for the entire study (Day 1 through Week 240). For patients randomized to placebo, two baselines will be used, one at randomization (Visit 2, Day 1) and the other at first dose of open-label ataluren (Visit 4, 48 weeks) for the analyses outlined below.

a) Analyses on the double-masked phase (Day 1 through Week 48).

Both placebo and ataluren will be presented and comparison will be made through 48 weeks between these two treatment groups. For the analyses of the double-masked phase, assessments at randomization (Visit 2 [Day 1]) will serve as baseline.

b) Analyses of the entire study (Visit 2, Day 1 through Week 240).

Efficacy will be presented based on two different baselines for placebo, one baseline at randomization (Visit 2) and the other baseline at Week 48 when placebo subjects first take open-label ataluren. Three analysis groups will be presented:

1. ataluren (all visits),
2. placebo (all visits) with Visit 2 assessments serving as baseline, and
3. combined groups with baseline at the first dose of ataluren (i.e., randomization -Visit 2 for ataluren patients and at the first dose of open-label ataluren (Visit 4, 48 weeks) for placebo patients).

Safety data for the entire study will be presented for the combined group for patients receiving ataluren.

By-subject listings will be created for each eCRF module. Summary tables for continuous variables will contain the following statistics: N, mean, median, standard deviation, standard error, minimum, maximum, and 95% confidence interval (CIs), as appropriate. Summary tables for categorical variables will include N, percentage, and 95% CIs on the percentage. Any CIs for proportions will be computed using normal approximation, if the number of the events is at least five. Otherwise, CIs using an exact method will be provided. Graphical techniques will be used when such methods are appropriate and informative. For safety summaries, CIs will not be presented, unless specified otherwise.

Transformations of the data may be explored if warranted by the distribution of the data.

Unless otherwise specified, all analyses will be two-sided at the 0.05 level of significance.

All analyses will be performed using SAS® (Version 9.0 or higher).

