The arithmetic difference between a post-baseline value and the baseline value:

Change from Baseline = (Post-baseline Value – Baseline Value)

Percentage Change from Baseline = [(Post-baseline Value – Baseline Value) / Baseline Value] x 100

End of Double-masked study period

End of double-masked study period is at Week 48 (day 337 ± 28 days), unless terminated early.

End of Study

End of study is at Week 144 (day 1008 ± 7 days), unless terminated early.

Early termination from study

Early termination would be assigned to the visit whose visit window included the termination date. In the event that an early termination visit does not fall within a nominal visit window, then the termination visit will be assigned to the visit closest to that date. If duplicate data result from the assignment of a termination visit, then the values measured last will be selected for analysis.

Enrollment date

Enrollment date will be assigned after confirmation of eligibility has been received from PTC Therapeutics, but not after the first day of study drug administration.

Study drug

Study drug in this study is ataluren (PTC124) or placebo.

Randomization date

Randomization date is the day the subject is assigned a randomization number on study Day 1.

Study Day 1

Day 1 is defined as the first day that study drug is administered to the subject.

Study Day

Day on study = Starting from Day 1

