Appendix A Schedule of Events

The types and timing of data to be recorded are summarized in Table 1 (Stage 1, double-masked period), Table 2 (Stage 2, open-label period), and Table 3 (open-label sub-study).

Table 1. Schedule of Events (Stage 1)

Protocol Activities		Screening				Double-Masked Treatment			
Day±Window	Week	-28	-4	1 ^a	1	169±28	24	337±28	48/ End of Stage 1 ^b
Visit		1		2		3			4
Informed consent		X							
Medical and ophthalmic history ^c		X							
Serum viral screen		X							
Physical exam		X		X					X
Height and weight		X		X		X			X
Vital signs		X		X		X			X
Ophthalmoscopy		X		X		X			X
Hematology, biochemistry, urinalysis		X				X			X
Serum β-HCG ^d		X		X		X			X
Study drug and diary dispensing				X		X			X
Study drug administration				X		X			X
Study drug compliance and return						X			X
Collect diary						X			X
Adverse events				X		X			X
Concomitant meds		X		X		X			X
MNREAD				X					X
████████████████████				X		X			X
Slit-lamp examination ^e				X		X			X
Slit-lamp photography				X		X			X
OCT				X		X			X
Fundus photography				X		X			X
Humphrey visual fields				X					X
BCVA (visual acuity and refraction) ^f		X		X		X			X
████████████████████				X		X			X
████████████████████				X		X			X
████████████████████ blood				X		X			X
sample for plasma PK ^g									If feasible (i.e., during surgery for glaucoma, cataracts, etc.)

Abbreviations: β -HCG, beta-human chorionic gonadotropin; BCVA, best corrected visual acuity; ETDRS, Early Treatment Diabetic Retinopathy Study; [REDACTED]; LEA, LEA Symbols Visual Acuity Test System; MNREAD, Minnesota Low Vision Reading (MNREAD) Acuity Charts; OCT, optical coherence tomography; PK, pharmacokinetic(s)

^a All study and laboratory assessments on the first day of treatment must be done prior to in-clinic administration of the first dose.

^b Open-label study drug administration will start at the end of Stage 1 (Visit 4/Week 48).

^c Should include capture of available historical values for ocular assessments included in this study, such as visual acuity, [REDACTED], etc.

^d Sample taken only for female subjects of childbearing potential.

^e Slit-lamp examination should precede [REDACTED] measurement.

^f Visual acuity and refraction will be assessed using the Early Treatment Diabetic Retinopathy Study (ETDRS) or an age-appropriate alternative (e.g., LEA).

Table 2. Schedule of Events (Stage 2)

Protocol Activities		Open-Label Treatment						End of Study)/ Early Termination ^a		Follow-Up ^b	

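### The SAP early-termination rule has no treatment-phase condition, so a termination visit after Visit 4 but inside the Week 48 window would replace masked MNREAD and BCVA values with post-switch ones

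*SAP*

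**What the plan says.** - **SAP 5, Early termination from study.** A termination visit goes to the window that contains it. If it is in no window, "then the termination visit will be assigned to the visit closest to that date". Then: "If duplicate data result from the assignment of a termination visit, then the values measured last will be selected for analysis". None of the three steps mentions treatment or stage.
- **SAP 5, End of Double-masked study period.** "End of double-masked study period is at Week 48 (day 337 ± 28 days), unless terminated early". The end is a day range, not Visit 4 or the first open-label dose.
- **Protocol 8.1.1.4.** At Visit 4 the site is to "Dispense open-label ataluren and Study Drug Dosing Diary". Footnote b to Table 1 in SAP Appendix A confirms that open-label dosing begins at that visit.
- **Protocol 8.2.** "any subject who discontinues early from the parent study should complete the Visit 8 assessments and return in 4 weeks for follow-up assessments". The Visit 8 list includes BCVA and MNREAD. Protocol 10 adds that when study drug is stopped, "the investigator is expected to capture all of the evaluations required at the EOS/ET Visit".
- **Protocol 11.3.** For the masked phase, "comparison will be made through 48 weeks between these two treatment groups". The placebo group's open-label baseline is tied to the first open-label dose at Visit 4. SAP 7.2 calls that baseline the Week 48 value.

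**The concern.** A termination visit can duplicate Week 48 data only if Visit 4 has already taken place, and Visit 4 is where masked treatment ends. So for a subject who has started open-label drug, the last-value clause discards a valid masked measurement in favour of one taken after the switch. For a placebo subject, a value obtained on ataluren would then be analysed under placebo. For an ataluren subject, it would be a later and unmasked value.

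The variables affected are the primary endpoint (Maximum Reading Speed) and both key secondary endpoints (Reading Accessibility Index and BCVA). SAP 2.5 reduces enrolment to 24, which under 2:1 allocation is about 8 placebo subjects, so one value carries weight.

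No other rule prevents this for efficacy data:
- The rule in SAP 7.5.1 that assigns events to a phase by date covers adverse events only.
- SAP 10.1 rules out imputation in the open-label period, but not reassignment of observed values.
- Protocol 11.3 confines the masked analysis to Day 1 through Week 48, but a reassigned visit would carry the Week 48 label.
- The masked analysis is run after the last subject completes Week 96 (SAP 2.4), so these visits should already be in the database.

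**Working it through.** **1. Visit days.** Target day = 7 × week + 1.
- Week 48: 7 × 48 + 1 = 337, as the SAP states. With ±28 days the window is days 309 to 365.
- Week 72: 7 × 72 + 1 = 505, as in SAP Appendix A Table 2. The window is days 477 to 533.
- Days 366 to 476 lie in no window.

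**2. Assignment under the SAP rule.**
- After Visit 4 and up to day 365: Week 48, by window.
- Days 366 to 420: Week 48, if closest means the nearest scheduled day of any visit. Day 420 is 420 − 337 = 83 days from Week 48 and 505 − 420 = 85 from Week 72.
- Day 421: an unresolved tie, (337 + 505)/2 = 421, 84 days each way.
- Day 422 onward: Week 72.

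**3. Gap between the Visit 4 value and the value that replaces it.**
- Within the window: at most 365 − 309 = 56 days, or 365 − 337 = 28 if Visit 4 is on its target day.
- Through the closest-visit step: up to 420 − 309 = 111 days, 420 − 337 = 83, or 420 − 365 = 55, for Visit 4 on day 309, 337 or 365.

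**4. Illustration: one replaced placebo value, no selection.** Assumptions that are not in the documents: 16:8 (24 subjects at 2:1), SD 1, all subjects MNREAD-evaluable, and the replacing value showing a fraction f of the drug effect. The effect size 1.06 and two-sided 0.05 come from SAP 7.1. The expected difference becomes 1.06 × (1 − f/8), which at f = 1 is 1.06 × 7/8 = 0.93. Power by simulation:

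| f | t-test, 16:8 | ANCOVA, 16:8 | ANCOVA, 24:12 |
|---|---|---|---|
| 0 | 65% | 60% | 81% |
| 0.25 | 62% | 57% | 79% |
| 0.5 | 59% | 55% | 77% |
| 1 | 52% | 48% | 73% |

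The ANCOVA columns use two covariates unrelated to outcome and residual SD 1. The 81% at 24:12 is close to the SAP's stated 80% for 36 subjects. At 16:8 and f = 1, diluting the mean difference alone gives t-test power of 54%. The simulated 52% is lower because one shifted value also adds spread within the arm. The row f = 1 is an upper bound, since it assumes the full effect within at most 111 days.

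**5. Illustration: with selection.** Same 16:8 t-test, one placebo value shifted by 1 SD.
- No drug effect, value 1 SD worse: two-sided rejection 5.4%, and rejection favouring ataluren 4.3% (nominal 2.5%).
- No drug effect, value 1 SD better: rejection favouring ataluren about 1.2%.
- Effect size 1.06, value 1 SD worse: power rises from 65% to 73%.

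**The case against.** **Days 366 to 420.** The SAP itself ends the masked period at day 337 ± 28, that is by day 365. An analyst could fairly exclude a later value on that ground. Closest is also undefined. MNREAD is not scheduled at Week 72, and if only MNREAD visits counted, the midpoint with Week 96 would be (337 + 673)/2 = day 505. This stands: a reader might infer that every termination up to day 420 is certainly caught, and the documents do not settle that. It does not help for days up to 365, which are inside both the window and the SAP's masked period.

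**Frequency.** A subject must complete Visit 4, start open-label drug and have a termination visit within weeks. The primary endpoint is touched only if that subject is MNREAD-tested, which Protocol 8.3.15 does not require under age 8. Only about a third of subjects are on placebo. This also stands.

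**Size.** The shifts are assumed, the mildest case costs 2 to 3 points of power, and under selection the planned two-sided test moves only from 5.0% to 5.4%. That is fair. The figures show how much one value can weigh; they do not predict the result. Fewer MNREAD-evaluable subjects would make one value weigh more.

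**Placebo open-label baseline.** A reader might infer that SAP 7.2 sets a wrong baseline. It does not: Protocol 11.3 makes the intent clear, and Protocol 11.8.2 does the same for laboratory data. Only the wording of SAP 7.2 is loose.

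**A programmer would choose Visit 4 anyway.** Possibly, but that would depart from the literal rule, and the choice would be made with the data in hand.

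**Conclusion.** The point holds. As written, SAP Section 5 would replace masked Week 48 MNREAD and BCVA values with post-switch values for a subject who completes Visit 4, starts open-label ataluren and has a termination visit by day 365. For days 366 to 420 it holds only on one reading of closest, and those days are outside the SAP's own masked period.

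A reader might go further and infer that the primary result will be biased, or biased towards ataluren. The documents do not support that. They give no expected number of such subjects, and it may be zero. The direction is open: a drug effect in the replacing value dilutes the difference, while a poor value in someone who stops soon after the switch inflates it. The power and rejection figures depend on the assumed 16:8 split and assumed shifts.

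This is a gap in the data-selection rule for the primary and key secondary endpoints. It is probably rare in effect, cheap to close, and best closed before unmasking.

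**What to change.** In SAP Section 5, state that:
1. an assessment made after the first open-label dose cannot be assigned to Week 48 and cannot replace a Visit 4 value;
2. the last-value clause applies only to assessments within the same treatment phase;
3. a post-switch termination assessment that falls in no open-label visit window is listed, or summarised as an open-label termination value. It should not be forced to Week 72: a day-340 value would be 505 − 340 = 165 days from that visit, which has no scheduled MNREAD.

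Do not redefine Week 48 as the last assessment before open-label dosing. In Stage 1, MNREAD is scheduled only at Visits 2 and 4, so that definition could turn a baseline value into a Week 48 observation. A missed Visit 4 assessment stays missing, and for the primary endpoint is handled under SAP 10.1 as written: LOCF as the primary method, with multiple imputation and the tipping-point analysis as sensitivity analyses.

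As a clarification only, say in SAP 7.2 that the placebo Week 48 baseline is the Visit 4 value measured before the first open-label dose, in line with Protocol 11.3.

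The cost is a few short clauses and one programming condition comparing assessment date with first open-label dose date. No data are lost.

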6 ANALYSIS POPULATIONS

6.1 Safety Analysis Population

The safety population will include all randomized subjects who receive at least 1 dose of study drug. Subjects will be analyzed as treated.

6.2 Intent-to-Treat Analysis Population

The intent-to-treat (ITT) population will include all randomized subjects who receive at least 1 dose of study drug. Subjects will be analyzed as randomized. The ITT population will be the primary efficacy population.

6.3 Efficacy Analysis Populations

The efficacy analysis population will include subjects for the ITT analysis population who have a baseline value and at least 1 post-baseline value. Subjects will be analyzed as treated. Analyses based on the efficacy analysis population will be supportive of those performed on the ITT population.

7 STATISTICAL METHODS OF ANALYSIS

All statistical analyses will be programmed using Statistical Software from SAS Institute (SAS®) software version 9.4 or later. Standard macros will be used in programming when possible. Testing and validation plans for all programs will be developed in accordance with Promedica International Inc. guidelines and will include independent programming of tables and analyses.

7.1 Sample Size

The study is planned to enroll a minimum of 36 subjects with nonsense mutation aniridia who are ≥ 2 years of age. This number of subjects should provide adequate information to evaluate the safety of ataluren in this population. For a statistical hypothesis test for any efficacy endpoint, the study will have 60% power to detect an effect size (i.e., standardized mean difference) of 0.85, or 80% power to detect an effect size of 1.06, at the 0.05 significance level (2-sided).

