### 8.3.14 [REDACTED]

### 8.3.15 MNREAD

Standard MNREAD Acuity Charts will be used to assess Reading Acuity, Critical Print Size, Maximum Reading Speed, and Reading Accessibility Index.

Reading speed is a strong predictor of visual ability and vision-related quality of life for patients with vision loss ([Hazel 2000](#)). For this reason, reading performance has been used as an outcome measure in clinical trials for judging the effectiveness of treatments ([Mahmood 2015](#)).

The Reading Accessibility Index summarizes an individual's access to text over the range of print sizes found in everyday life. The Reading Accessibility Index relies on a simple calculation: averaging the reading speed measured over the 10 largest print sizes on the MNREAD and normalizing it by the mean value for a group of normally sighted young adults ([Calabrese 2016](#)). The Reading Accessibility Index is a single-valued measure that depends on both the range of accessible print sizes for a subject, and the subject's speed of reading within this range. Because the Reading Accessibility Index is normalized by the value for a group of normally sighted young adults (aged 18–39 years), a Reading Accessibility Index of 1.0 represents normal performance for this age group. Values less than 1.0 mean reduced accessibility to printed text within the range of print size encountered in daily life ([Calabrese 2016](#)).

The MNREAD Acuity Charts are continuous-text reading-acuity charts suitable for measuring reading acuity and reading speed of normal and low-vision patients. The study manual should be referenced for detailed instructions.

The reading level of the MNREAD Acuity Charts is approximately 2nd to 3rd grade level. It is estimated that subjects around the age of 8 years or older will be able to complete this assessment. Any subject less than the age of 8 years old will not be required to have this study assessment administered.

Three charts will be utilized for the MNREAD testing; one chart will be used for OD, one chart for OS, and the third chart for OU. It is imperative that the charts used for the monocular and binocular testing be changed out to decrease the likelihood of memorization of the text sentences by the subject.

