### **8.3.21 Best Corrected Visual Acuity (BCVA) and Refraction**

BCVA and refraction will be assessed using the Early Treatment Diabetic Retinopathy Study (ETDRS).

Refraction and testing of BCVA must be performed before the subject's eyes are dilated and prior to fundus photography and OCT imaging. Manifest refraction must precede the BCVA testing. For this study, it is estimated that children at the age of 6 or older will be able to be tested with a subjective refraction and ETDRS charts.

Age-appropriate alternative visual acuity chart (e.g., LEA symbols) will be used for any subject under the age of 6; however, the same chart should be used throughout the duration of the study.

The study manual should be referenced for detailed instructions.

[REDACTED]

- [REDACTED]
- [REDACTED]

[REDACTED]

[REDACTED]

[REDACTED]

[REDACTED]

- [REDACTED]
- [REDACTED]

[REDACTED]

[REDACTED]

[REDACTED]

[REDACTED]

[REDACTED]

[REDACTED]

[REDACTED]

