## 11 STATISTICS

### 11.1 Sample Size

The study is planned to enroll a minimum of 36 subjects with nonsense mutation aniridia who are  $\geq 2$  years of age. This number of subjects should provide adequate information to evaluate the safety of ataluren in this population. For a statistical hypothesis test for any efficacy endpoint, the study will have 60% power to detect an effect size (i.e., standardized mean difference) of 0.85, or 80% power to detect an effect size of 1.06, at the 0.05 significance level (two-sided).

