2.4 Study Design

This is a Phase 2, multicenter, stratified, randomized, double-masked, placebo-controlled study with a 4-week screening period, a 144-week treatment period, an optional 96-week open label sub-study, and a 4-week post-treatment follow-up period (either study completion or early termination). A minimum of 36 subjects with nonsense mutation aniridia who are ≥ 2 years of age are planned for enrollment into this study at investigator sites in US and Canada.

During the 4-week screening period, subjects will be assessed for eligibility.

Eligible subjects will enter the 144-week treatment period consisting of two stages:

- Stage 1 (Weeks 1 to 48) during which subjects will receive either ataluren or placebo in a masked fashion;
- Stage 2 (Weeks 49 to 144) during which subjects will receive open-label ataluren.

Eligible subjects will be randomized in a masked 2:1 fashion to either ataluren or placebo. Randomization will be stratified by age: ≤ 10 years versus > 10 years. Masked study drug will be dosed three times a day: 10 mg/kg in the morning, 10 mg/kg at midday, and 20 mg/kg in the evening for 48 weeks. Subjects (or parent/legal guardian) will record each dose on a diary card provided by PTC Therapeutics.

After completion of the Stage 1 (Week 48), subjects will be eligible for an additional 96 weeks of open-label ataluren treatment. Subjects who received ataluren during Stage 1 will continue to receive ataluren; subjects who had been randomized to placebo will receive ataluren during Stage 2

There will be an optional sub-study at the end of the Stage 2 Open-Label Extension. Subjects will be able to consent to receive an additional 96 weeks of ataluren treatment, returning to the clinic every 24 weeks. The assessments to be conducted are outlined in the schedule of events. Subjects who choose not to participate in the sub-study will be required to complete the Post-treatment follow-up visit at the end of the Stage 2 Open-Label Extension.

[figure not shown]
The start of the sub-study will require prior approval of a protocol amendment from applicable Institutional Review Boards and will continue for 96 week or until commercial availability of ataluren for this indication, whichever is first, or until a positive risk-benefit assessment in this indication is not demonstrated.

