2.5 Sample Size

The study was planned to enroll a minimum of 36 subjects with nonsense mutation aniridia who are ≥ 2 years of age. This number of subjects has been reduced to 24 and should provide adequate information for an initial evaluation the efficacy safety of ataluren in this population.

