7.7 Efficacy Analysis

All efficacy analyses will be conducted in both ITT population as the primary analysis. Visual acuity, corneal keratopathy, and iris area will also be analyzed using the efficacy analysis population as a supportive analysis.

The primary efficacy analysis will be by analysis of covariance (ANCOVA) where baseline Maximum Reading Speed (OU) and age will be included as covariates, with treatment as a fixed effect. LS means for the two treatment arms will be provided along with 95% confidence intervals.

To assess treatment effect on the change from baseline in secondary endpoints, general linear models/ANCOVA models, with baseline adjustment and treatment as factors will be used. For the analysis of MNREAD endpoints, age will be included as a continuous covariate; all other secondary endpoints will include age stratum as a factor in the model.

To adjust for other potential effects, some other appropriate statistical models, e.g., ANCOVA models, and/or mixed effect models, may be explored. The p-value of testing treatment difference will be provided. The trend of assessments overtime may be assessed. A summary of the efficacy endpoints listed above will also be provided by visit to assess the trend. Tests of trend, if performed, would include repeated measures over visits with an appropriate covariance structure fitted (first order autoregressive). The effect of linear time would be fit along with its product with treatment to test for differences in trend over time between the two treatment arms. If missing Week 48 assessments for the primary efficacy endpoint exist, sensitivity analyses will be conducted. The reasons of missing will be reported. Analysis results for data with and without imputations (using methods defined in Section 10.1) will be compared.

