8 CHANGES FROM PROTOCOL-SPECIFIED ANALYSES

Modifications to the planned statistical analyses should be minimized. Nonetheless, the data obtained from the study may indicate that the planned analyses are inappropriate or that additional analyses need to be performed. The study report will document any deviations from the planned analyses.

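### SAP 7.1 still quotes the power for 36 subjects after SAP 2.5 cuts enrolment to 24; at 16:8 without covariate gain, power is about 47% and 65%, not 60% and 80%

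*SAP*

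**What the plan says.** Protocol 11.1 plans at least 36 subjects and states: "For a statistical hypothesis test for any efficacy endpoint, the study will have 60% power to detect an effect size" of 0.85, or 80% power at 1.06, two-sided 0.05. SAP 7.1 repeats this for 36: "the study will have 60% power to detect an effect size (i.e., standardized mean difference) of 0.85".

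SAP 2.5 recalls the plan for 36 and then says: "This number of subjects has been reduced to 24 and should provide adequate information for an initial evaluation". It gives no power or detectable effect for 24. SAP 2.4 still has "A minimum of 36 subjects with nonsense mutation aniridia" planned for enrolment, with 2:1 randomization stratified by age.

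The primary model is in SAP 7.7: "baseline Maximum Reading Speed (OU) and age will be included as covariates, with treatment as a fixed effect". Neither document gives an R-squared, a dropout allowance or the test behind the power figures. SAP Section 8, whose heading concerns changes from the protocol-specified analyses, lists none and says: "The study report will document any deviations from the planned analyses".

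Two assessment rules affect how many subjects can contribute. For MNREAD (Protocol 8.3.15): "Any subject less than the age of 8 years old will not be required to have this study assessment administered". For visual acuity (Protocol 8.3.21): "Age-appropriate alternative visual acuity chart (e.g., LEA symbols) will be used for any subject under the age of 6".

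**The concern.** Sections 2.4, 2.5 and 7.1 are all current SAP text, and they give two different sample sizes. The power sentence goes with the larger one. A reader who turns to the statistical methods section learns that the trial has 80% power for a difference of 1.06 SD, when the SAP has already cut enrolment by a third.

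The main consequence is for reading a non-significant result. Under the fixed sequence in SAP 7.8, failure on the primary endpoint stops formal testing of both key secondary endpoints. Someone who believes the trial had 80% power would take such a failure as stronger evidence against an effect of that size than it is.

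The claim to cover any efficacy endpoint is also too wide. MNREAD supplies the primary endpoint and the first key secondary (Reading Accessibility Index). Entry is open from age 2, but children under 8 need not take the test.

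**Working it through.** **Inputs.** N = 36 (Protocol 11.1, SAP 2.4, SAP 7.1) or 24 (SAP 2.5). Allocation is 2:1 (SAP 2.4), so 24:12 or 16:8 if exact. Two-sided alpha is 0.05; effect sizes d are 0.85 and 1.06 (SAP 7.1). Assumed because the documents are silent: two-sample t-test, no losses, no covariate gain.

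**Formula.** Power is the probability that a noncentral t variable with n1 + n2 − 2 degrees of freedom and noncentrality d × √(n1·n2/(n1+n2)) exceeds the two-sided critical value.

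**The plan's own figure, N = 36.** √(24·12/36) = 2.828, df = 34, critical value 2.032.
- d = 0.85: noncentrality 2.404, power 64.7%.
- d = 1.06: noncentrality 2.998, power 83.0%.

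The stated 60% and 80% are thus not exactly the t-test power at 24:12; they are a little lower. They fit about 33 evaluable subjects (22:11 gives 60.7% and 79.4%) or a Wilcoxon test at 24:12 (simulated 61.3% and 80.8%). The documents name neither basis. For 36 the statement is, if anything, cautious.

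**N = 24.** √(16·8/24) = 2.309, df = 22, critical value 2.074.
- d = 0.85: noncentrality 1.963, power 46.7%.
- d = 1.06: noncentrality 2.448, power 64.8%.
- Solving for d: 1.00 for 60% power and 1.27 for 80%.

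On the same t-test basis, the cut from 36 to 24 costs about 18 points at each effect size (64.7 − 46.7 = 18.0; 83.0 − 64.8 = 18.2).

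**Other methods at 16:8.** The normal approximation gives 50.1% and 68.7%; Wilcoxon simulation gives 43.1% and 60.2%. None reaches 60% and 80%.

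**Planned ANCOVA at 16:8.** Two covariates leave df = 20. If d is in residual-SD units, power is 46.4% and 64.4%. If d is in raw-SD units, the noncentrality is divided by √(1 − R²):

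| R² | d = 0.85 | d = 1.06 |
|---|---|---|
| 0.10 | 50.4% | 69.0% |
| 0.20 | 55.1% | 74.0% |
| 0.30 | 60.7% | 79.5% |
| 0.50 | 75.2% | 90.8% |

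Reaching 60% at 0.85 needs R² = 0.288; reaching 80% at 1.06 needs R² = 0.309.

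**MNREAD, illustration only.** The documents give no age distribution, so these evaluable numbers are assumptions (unadjusted t-test, 2:1):

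| Evaluable | Power at 1.06 | d for 80% power |
|---|---|---|
| 21 (14:7) | 58% | 1.37 |
| 18 (12:6) | 51% | 1.49 |
| 12 (8:4) | 35% | 1.90 |

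**The case against.** **Nothing downstream uses the power sentence.** No estimate, p-value, interval, testing order or imputation rule depends on it, and SAP 2.5 discloses the cut openly and claims only an initial evaluation. On this view the defect is stale text. That is right about the analysis. It does not make the sentence true: 7.1 is the only place in the SAP where power is stated, and it is wrong for the trial being run.

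**The comparison mixes bases.** Setting 47% and 65% against 60% and 80% compares a t-test at 24 with figures of unstated origin. This stands, but a common basis does not help the plan: the t-test falls from 65% and 83%, and the missed rate at 1.06 rises from about 17% to 35%. If the stated figures allowed for about 7% attrition, the counterparts at 24 are about 44% and 61%.

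**Covariate adjustment may recover the loss.** It could, at an R² near 0.3 on the raw-SD scale. No document states an R², and 7.1 does not invoke one, so 47% and 65% are conditional on no gain.

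**The 16:8 split is assumed.** Stratified allocation may not land exactly there. By the same formula, 17:7 gives 44% and 62%, and 15:9 gives 49% and 67%. The restated sentence should name the split as a condition.

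**The MNREAD shortfall is inferred.** Under-8s are not required to take the test, but they are not barred from it. A number below 24 is likely, not established, which is why a count is needed.

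**Section 8 concerns analyses, not enrolment.** This is fair as far as it goes. An entry there is a matter of traceability, less important than correcting 7.1.

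**Conclusion.** The point holds. The SAP carries two sample sizes, and its only power statement belongs to the one it has dropped. With 24 subjects at exactly 2:1, a t-test at two-sided 0.05, no losses and no covariate gain, power is about 47% at 0.85 and 65% at 1.06. A true difference of 1.06 SD would be missed about 35% of the time, against the 20% that SAP 7.1 implies. The 80% detectable difference is 1.27 SD.

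For the primary and other MNREAD endpoints these are best-case unadjusted figures at that split, since they require all 24 subjects to have MNREAD data. BCVA does not face this age restriction, because under-6s have an alternative chart. The validity of the test and the estimates is not in question; the stated power and detectable effect are. Because the sentence is wrong for the trial being run and cheap to correct, it should be corrected before the results are read.

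**What to change.** 1. Make SAP 2.4, 2.5 and 7.1 agree on 24.
2. Replace the power sentence in SAP 7.1, for example: *With 24 subjects randomized 2:1 (16 ataluren and 8 placebo if the ratio is exact), a two-sample t-test at the two-sided 0.05 level, assuming no covariate gain and no losses, has about 47% power for a standardized mean difference of 0.85 and 65% for 1.06; differences of 1.00 and 1.27 give 60% and 80% power. These figures apply to efficacy endpoints other than MNREAD.*
3. Add a separate line for the MNREAD endpoints, including the primary, computed from the masked count of subjects with a baseline MNREAD.
4. State whether the effect size is in raw-SD or residual-SD units. If a gain from ANCOVA is claimed, give the assumed R-squared and its source.
5. Record the reduction from 36 to 24 in SAP Section 8.

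The cost is SAP wording and one masked count. No patients are added, and the test, alpha and populations stay as they are. The stated figures become less favourable.
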